7.2. Adverse Events Analyses

Adverse events analyses including the analysis of adverse events (AEs), Serious (SAEs) and other significant AEs will be based on GSK Core Data Standards. The details of the planned displays are provided in [Appendix 10: List of Data Displays](#).

Adverse events (AEs) will be graded according to the Common Terminology Criteria for Adverse Events (CTCAE v4.0). Adverse events will be coded to the PT level using the MedDRA dictionary. The relationship of AE system organ class, preferred term, and verbatim text will be listed.

A summary of number and percentage of subjects with any adverse events by maximum grade will be produced. AEs will be sorted by System Organ Class (SOC) and Preferred term (PT) in descending order of total incidence. The summary will use the following algorithms for counting the subject:

- **Preferred term row:** Subjects experiencing the same AE preferred term several times with different grades will only be counted once with the maximum grade.
- **Any event row:** Each subject with at least one adverse event will be counted only once at the maximum grade no matter how many events they have.

In addition, the frequency and percentage of AEs (all grades) will be summarized and displayed in descending order of total incidence by SOC and PT. In the SOC row, the number of subjects with multiple events under the same system organ class will be counted once.

The relationship between MedDRA SOC, PT, and Verbatim Text will be listed.

Summary tables will be provided for study treatment-related AEs. A study treatment-related AE is defined as an AE for which the investigator classifies the relationship to study treatment as “Yes”. A worst-case scenario approach will be taken to handle missing

relatedness data, i.e. the summary table will include events with the relationship to study treatment as ‘Yes’ or missing. Two summary tables for treatment-related AEs will be provided:

- Summary of treatment-related AE by maximum toxicity grade. For each toxicity grade, treatment-related AEs will be displayed in descending order of total incidence by PT only.
- Summary of treatment-related AE by frequency. Treatment-related AEs will be displayed in descending order of total incidence by PT only.

A summary of non-serious AEs that occurred in strictly 5% of the subjects or above will be provided (no rounding for the percentage will be used in terms of 5% threshold, e.g., event with 4.9% incidence rate should not be included in this table). The summary will be displayed by System Organ Class (SOC) and Preferred Term (PT) in descending order of total incidence.

A listing of all AEs will be provided. A listing of adverse events recorded as dose-limiting toxicities will be provided.

A listing of deaths will be generated to provide subject-specific details on subjects who died.

All serious adverse events (SAEs) will be tabulated based on the number and percentage of subjects who experienced the event. The summary tables will be displayed by SOC and PT in descending order of total incidence.

Separate supportive listings with subject-level details will be generated for fatal and non-fatal SAEs, respectively. The fatal and non-fatal SAEs will be listed by dose level and subjects, including the relationship with treatment. A study treatment-related SAE is defined as an SAE for which the investigator classifies the relationship to study treatment as “Yes”.

7.3. Clinical Laboratory Analyses

Laboratory evaluations including the analyses of Chemistry laboratory tests, Haematology laboratory tests, and liver function tests will be based on GSK Core Data Standards. The details of the planned displays are in [Appendix 10: List of Data Displays](#).

The assessment of laboratory toxicities will examine the following laboratory tests:

Hematology			
Platelet Count	RBC Indices:		Automated WBC Differential:
Red Blood Cell (RBC) Count	Mean Corpuscular Volume (MCV)		Neutrophils
White Blood Cell (WBC) Count (absolute)	Mean Corpuscular Hemoglobin (MCH)		Lymphocytes
Reticulocyte Count	Mean Corpuscular Hemoglobin Concentration (MCHC)		Monocytes
Hemoglobin			Eosinophils
Hematocrit			Basophils
Clinical Chemistry			
Blood Urea Nitrogen (BUN)	Potassium	Alanine Aminotransferase (AST)	Total and direct bilirubin
Creatinine	Chloride	Aspartate Aminotransferase (ALT)	Uric Acid
Sodium	Calcium	Alkaline phosphatase	Total Protein
Magnesium	Glucose	Lactate Dehydrogenase (LDH)	
Follicle Stimulating Hormone (FSH) and estradiol (as needed in women of non-child bearing potential and all peri menopausal women)			
Pregnancy test for females (serum B-HCG at screening, Urine or serum B-HCG during Continuation Phase)			

Laboratory grades will be evaluated using CTCAE v4.0. However, some tests are not graded using CTCAE.

For hematology, Red Blood Cell (RBC) is not gradable by CTCAE v4.0.

For clinical chemistry, BUN and creatinine clearance are not gradable by CTCAE v4.0. For sodium, potassium, calcium, glucose, and magnesium there will be two bi-directional parameters (hyper and hypo) created and the tests will be graded by CTCAE v4.0 in both directions.

Separate summary tables for hematology and chemical chemistry will be produced as detailed below. Liver function and pancreatic laboratory tests will be included with chemical chemistry.

Summary of worst case toxicity grade of lab values increase from baseline grade across all scheduled visits will be generated by dose level for all the lab tests that are gradable by CTCAE v4.0. Any increase to a higher grade from baseline will be summarized. Missing baseline grade will be assumed as grade 0. For laboratory tests that are graded for both low and high values, summaries will be done separately and labeled by direction, e.g., sodium will be summarized as hyponatremia and hypernatremia.

For lab tests that are not gradable by CTCAE v4.0, summaries of worst case change from baseline with respect to normal range will be generated. Decreases to low, changes to normal or no changes from baseline, and increases to high will be summarized for the worst case post-baseline. If a subject has a decrease to low and an increase to high during the same time interval, then the subject is counted in both the “Decrease to Low” categories and the “Increase to High” categories.

Detailed derivation of baseline assessment is specified in Section [5.2](#).

Unless otherwise specified, the denominator in percentage calculation at each scheduled visit will be based on the number of subjects with non-missing value at each visit.

Supporting listings of haematology and chemistry laboratory tests will be provided.

A character lab value starting with ‘<X’ or ‘>X’ will be displayed in listings, but will not be imputed with a numeric value thus will not be included for summaries.

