5.2. Baseline Definitions

For laboratory data, baseline values are defined as the most recent, non-missing value from a local laboratory prior to the first dose of study treatment.

For ECG analyses, subject level baseline is defined as the mean of triplicate Cycle 1 Day 1 (C1D1) pre-dose QTc results.

Parameter	Study Assessments Considered as Baseline			Baseline Used in Data Display
	Screening	Day -1	Day 1 (Pre-Dose)	
Efficacy				
Disease Assessment	X			Screening
Safety				
Vital Signs	X		X	Day 1 Pre-dose if collected, otherwise, use screening
ECG	X		X	Mean of triplicate pre-dose measurements on Day 1, if not available, use mean values at screening
Clinical Chemistry, Hematology	X		X	Day 1 Pre-dose if collected, otherwise, use screening

Parameter	Study Assessments Considered as Baseline			Baseline Used in Data Display
	Screening	Day -1	Day 1 (Pre-Dose)	
Coagulation	X			Screening
PK/PD				
PK Concentration			X	Day 1 Pre-dose
PD Biomarker			X	Day 1 Pre-dose

Unless otherwise stated, if baseline data is missing no derivation will be performed and the baseline data will be set to missing.

The baseline definition will be footnoted on all change from baseline displays.

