7.3.1. Liver Function Analyses

Summaries of hepatobiliary laboratory events including possible Hy’s law cases will be provided in addition to what has been described above.

Possible Hy’s law cases are defined as any elevated (ALT $\geq 3 \times$ ULN **and** overall bilirubin $\geq 2 \times$ ULN (with direct bilirubin $\geq 35\%$ of total bilirubin, if direct bilirubin is measured) **OR** (ALT $\geq 3 \times$ ULN **and** INR > 1.5 , if INR is measured). Note that INR measurement is not required and the threshold value stated will not apply to patients receiving anticoagulants.

A listing of liver function tests for subjects meeting Hy’s law will be generated. A listing of subjects with liver function test toxicity grade ≥ 3 will also be provided.

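### Leaving laboratory results reported as `<X` or `>X` out of the worst-case summaries can understate a subject's worst result even where the reporting limit alone establishes the category

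*SAP*

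**What the plan says.** SAP Section 7.3 gives the rule for laboratory results that carry an inequality sign. They "will be displayed in listings, but will not be imputed with a numeric value thus will not be included for summaries". No table is exempted.

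The summaries to which the rule applies are all categorical:

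- Gradable tests (Tables 3.8 and 3.9): "Summary of worst case toxicity grade of lab values increase from baseline grade across all scheduled visits will be generated by dose level".
- Tests without a CTCAE grade (Table 3.11): "summaries of worst case change from baseline with respect to normal range will be generated".
- Liver (Table 3.10, Section 7.3.1): "Summaries of hepatobiliary laboratory events including possible Hy’s law cases will be provided".

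Two other rules bear on baseline. Section 7.3 states "Missing baseline grade will be assumed as grade 0". Section 5.2 defines the laboratory baseline in its text as "the most recent, non-missing value from a local laboratory prior to the first dose of study treatment", and in its table as "Day 1 Pre-dose if collected, otherwise, use screening".

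Changes in clinical laboratory parameters are among the Part 1 primary endpoints (Section 2.2).

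**The concern.** A result reported as `>X` or `<X` is censored, not missing: its direction is known and a bound is known. Omitting it is defensible when computing a mean or standard deviation, because those need a number. A worst-case category often does not. If X is already past the cut-off, the inequality proves the category.

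Whether a result is excluded depends on its size. When the censored result lies on the toxic side it is likely to be the subject's most extreme value, so the tables meant to show the worst value would leave it out and show the next-worst instead. The bias in post-baseline toxicity is downward.

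At stake are the by-dose laboratory tables for a primary safety endpoint in very small cohorts. So is the selection of subjects for Listing 28 (liver function toxicity of Grade 3 or higher) and Listing 29 (possible Hy's law). The SAP does not say how a result without a numeric value can trigger either selection.

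**Working it through.** The plan states no figure to reproduce. The check traces the rule through one worked example and then scales it.

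**1. Post-baseline worst case, single analyte**

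Inputs from the SAP:
- ALT upper limit of normal (ULN) = 34 IU/L, from the mock listing SAFE_L2 in Appendix 11 (illustrative).
- ALT criterion of at least 3 × ULN, from Section 7.3.1. Threshold: 3 × 34 = 102 IU/L.

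Assumptions, because the SAP gives no reporting limits:
- X = 1000 IU/L.
- ALT results of 30, 60, `>1000`, 60, all at scheduled visits.

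| Handling of `>1000` | Worst ALT | Multiple of ULN | At least 3 × ULN? |
|---|---|---|---|
| Excluded (SAP rule) | 60 | 60/34 = 1.8 | No |
| Taken at its limit | more than 1000 | more than 1000/34 = 29.4 | Yes |

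For this series the answer reverses for any X of 102 or more. If X were below 102, the bound alone would not prove the criterion.

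**2. Size if one subject is affected**

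This assumes that the censored result is the subject's only scheduled result in that category. Section 2.3 gives one subject per dose level in accelerated titration, then 3+3, and 30 to 40 subjects in Part 1.

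| Subjects | True proportion | Under the rule |
|---|---|---|
| 1 | 1/1 = 100% | 0 |
| 3 | 1/3 = 33.3% | 0 |
| 6 | 1/6 = 16.7% | 0 |
| 30 | 1/30 = 3.3% | 0 |
| 40 | 1/40 = 2.5% | 0 |

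If the subject has another numeric result in the same category, nothing is lost. If the next-worst result is only somewhat milder, the subject moves down by fewer grades.

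**3. Baseline**

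Take a censored Day 1 pre-dose result on the toxic side. Its fate depends on how Section 5.2 is read:

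- *Counted as missing, numeric screening value available:* screening supplies a real grade and no harm follows.
- *Counted as missing, no other usable pre-dose value:* the baseline grade is missing and becomes Grade 0.
- *Counted as collected and non-missing, but left ungraded:* screening is not consulted and the baseline grade becomes Grade 0.

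In the last two cases an abnormal baseline is recorded as Grade 0, so a later result at the same grade appears as a worsening. That error runs upward, opposite to the one in step 1.

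**4. Direct-to-total bilirubin ratio**

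A bound settles the 35% condition only sometimes. With direct bilirubin reported as `<X` and a numeric total T, the ratio is below X/T. If X/T is 0.35 or less, the condition is certainly not met; if X/T exceeds 0.35, it is undetermined. With a numeric direct value D and total `>X`, the ratio is below D/X and the same logic applies. Substituting X as if it were the observed value could therefore wrongly satisfy the 35% condition.

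**The case against.** The strongest case for leaving the rule alone is that it is disclosed and loses nothing from the record. The raw results remain in Listings 11 and 12. Adverse events reported by investigators are graded and tabulated separately, with dose-limiting toxicities and events of Grade 3 or higher in their own listings. Part 1 is descriptive, the report is an abbreviated one for a terminated study, and escalation decisions used in-stream data. Neither the reporting limits nor the number of such results is given, and many may lie on the harmless side of the test.

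Much of this stands. It limits how far the effect can be pressed, and it rules out saying that the values are deleted from the report. It does not rescue the worst-case tables. They are the planned by-dose display of laboratory change, and a reader would have to search the raw listings to find that a known extreme was left out.

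Two stronger readings are tempting. One is that every censored baseline becomes Grade 0. The documents do not say so: Section 5.2 may lead back to a numeric screening value. The other is that a censored direct bilirubin counts as not measured and so switches off the 35% condition. The wording "if direct bilirubin is measured" does not support that, because a result below a limit has been measured. Were it handled that way, the effect would be to flag too many possible Hy's law cases, not to hide them.

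**Conclusion.** The point holds for post-baseline worst-case categories. Followed as written, Section 7.3 can leave a subject's most extreme result out of Tables 3.8 to 3.11 when the reporting limit alone proves the grade, flag or threshold. The resulting bias is downward and depends on the value.

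The size is conditional. It is at most one subject in the relevant proportion for each affected subject, and zero where X lies short of the cut-off, the result is on the harmless side, or another numeric result falls in the same category. How many results are affected cannot be determined from the SAP.

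The baseline effect is a possibility that the SAP leaves open, not a consequence it fixes, and it would overstate worsening. The two effects should not be assumed to cancel. The rule merits correction before the tables are produced because it is explicit, bears on a primary endpoint and is easily put right.

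**What to change.** Replace the sentence in Section 7.3 with a rule along these lines:

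- In the categorical laboratory summaries, and in the selection for Listings 28 and 29, give a `<X` or `>X` result the grade, normal-range flag or threshold status that its limit establishes. Read the inequality as strictly beyond X, so that a limit equal to a cut-off is not under-graded.
- Where the limit does not fix the grade exactly, assign the minimum grade it implies and footnote it. Where the limit establishes no category, flag the result as indeterminate and state how it enters the denominator.
- Apply the same rule at baseline and post-baseline, and say in Section 5.2 that a censored pre-dose result is not missing.
- In the hepatobiliary summary, apply it to the single-analyte criteria for ALT, total bilirubin and INR, keeping the existing INR exception for patients on anticoagulants.
- Do not compute the direct-to-total bilirubin ratio from a bound unless the bound determines whether 35% is met; otherwise mark it as indeterminate.

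The cost is a short SAP edit, minor programming and a footnote on Tables 3.8 to 3.11. No new data are needed.

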7.3.1. Liver Function Analyses

Summaries of hepatobiliary laboratory events including possible Hy’s law cases will be provided in addition to what has been described above.

Possible Hy’s law cases are defined as any elevated (ALT $\geq 3 \times$ ULN **and** overall bilirubin $\geq 2 \times$ ULN (with direct bilirubin $\geq 35\%$ of total bilirubin, if direct bilirubin is measured) **OR** (ALT $\geq 3 \times$ ULN **and** INR > 1.5 , if INR is measured). Note that INR measurement is not required and the threshold value stated will not apply to patients receiving anticoagulants.

A listing of liver function tests for subjects meeting Hy’s law will be generated. A listing of subjects with liver function test toxicity grade ≥ 3 will also be provided.

7.4. Other Safety Analyses

The analyses of non-laboratory safety test results including ECGs and vital signs will be based on GSK Core Data Standards, unless otherwise specified. The details of the planned displays are presented in [Appendix 10: List of Data Displays](#).

Vital Signs

Listing of vital signs including Systolic BP, diastolic BP, heart rate, body temperature, height and weight at each scheduled visit will be provided.

ECOG (Eastern Cooperative Oncology Group) Performance Status

A summary of worst case post-baseline ECOG status shift from baseline among all visits by dose level will be provided. A supporting listing including performance status and change from baseline will also be provided.

ECG

A summary of the number and percentage of subjects who had normal and abnormal ECG findings will be displayed by scheduled visits as well as for the worst case post-baseline for each dose level. A listing of abnormal ECG findings will be provided. ECG interval values will also be listed.

The mean of ECG values at each collection point will be used for ECG analyses

Summary of the worst case QTc (QTcF and QTcB) post-baseline values relative to baseline will be provided by dose level. The QTc values (QTcF and QTcB) will be

rounded to the integer and the values will be categorized into the following ranges: Grade 0 (<450), Grade 1 (450-480), Grade 2 (481-500), and Grade 3 (≥ 501).

Summary of the worst case QTc (QTcF and QTcB) increase from baseline by dose level will be provided. The categories of 'Increase of ≤ 30 msec' 'Increase of 31-60 msec' and 'Increase of > 60 msec' will be used. A summary of change in QTc value will display the number and percentage of subjects with a change within each category in the worst case post-baseline among all visits.

Baseline results are defined by the nearest timepoint prior to first dose. The baseline QTc value is determined by the mean of the triplicate Cycle 1 Day 1 (C1D1) pre-dose QTc results. If these results are not available, then the mean of QTc of the screening triplicate QTc results would be used. Subjects with a missing baseline value will be assumed to have a normal baseline value.

LVEF (Left Ventricular Ejection Fraction)

LVEF results will be listed with subject level details including absolute change from baseline. Only the post-baseline assessments that used the same method (ECHO or MUGA) as the baseline assessments will be used to derive the change from baseline.

8. EFFICACY ANALYSES

The efficacy analyses will be based on the All Subjects population. All efficacy analyses will be descriptive, graphically presented (where appropriate) and listed. All summaries and data listings will use treatment labels as specified in Section 5.1. All summaries will be presented by dose level and overall.

A summary of investigator-assessed best response with confirmation will be presented by tumor types (solid tumors and Lymphoma). Subjects with Not Evaluable or missing response will be treated as non-responders; and they will be included in the denominator when calculating the percentage. To be assigned a status of complete response or partial response, all responses must be confirmed by repeat assessments performed no less than four weeks after the criteria for CR or PR were met (Protocol Appendix 4 (Revised Response Criteria for Malignant Lymphoma (RRCML) and Appendix 5 (RECIST 1.1)).

The investigator assessment of target lesion, non-target lesion and new lesion will be listed, separately. A listing of investigator-assessed confirmed tumor response will be provided. Waterfall plots of maximum investigator-assessed tumor size reduction from baseline will be generated for solid tumor subjects including prostate cancer and lymphoma subjects, respectively.

Details of the planned displays are provided in [Appendix 10: List of Data Displays](#).

9. PHARMACOKINETIC ANALYSES

9.1. Primary Pharmacokinetic Analyses

9.1.1. Endpoint / Variables

9.1.1.1. Drug Concentration Measures

The GSK2816126 concentration-time data will be summarized by planned time point and dose cohort. Standard summary statistics will be calculated (i.e. mean, standard deviation, median, minimum and maximum).

Refer to [Appendix 5: Data Display Standards & Handling Conventions \(Section 12.5.3 Reporting Standards for Pharmacokinetic\)](#)

9.1.1.2. Derived Pharmacokinetic Parameters

Pharmacokinetic parameters will be calculated by standard non-compartmental analysis according to current working practices and using the currently supported version of WinNonlin Version 6.3. All calculations of non-compartmental parameters will be based on actual sampling times.

Pharmacokinetic parameters listed will be determined from the plasma concentration-time data, as data permits.

Parameter	Parameter Description
AUC(0-t)	Area under the concentration-time curve from time zero to the time of the last quantifiable concentration (C(t)) will be calculated using the linear trapezoidal rule for each incremental trapezoid and the log trapezoidal rule for each decremental trapezoid.
AUC(0-∞)	Area under the concentration-time curve extrapolated to infinity will be calculated as: $AUC = AUC(0-t) + C(t) / \lambda_z$ This will be calculated for Cycle 1 Day 1 only
AUC(0-tau)	Area under the concentration-time curve from time zero to the predose of the next dose.
Cmax	Maximum observed concentration, determined directly from the concentration-time data.
tmax	Time to reach Cmax, determined directly from the concentration-time data.
t½	Apparent terminal half-life will be calculated as: $t\frac{1}{2} = \ln 2 / \lambda_z$
λz	Apparent terminal phase elimination rate constant
Cτ	Trough (pre-dose) concentration at the end of dosing interval on the specified days (Days 8, 15 and 22 where available).
CL	Clearance
V	Volume

NOTES:

Additional parameters may be included as required.

